11.7.8 Other

Not applicable.

12 DISCONTINUATION OF THE STUDY

Aptalis Pharma US, Inc. may terminate the study for safety, ethical or administrative reasons at any time. In such cases, all Investigators have to be notified immediately in writing, outlining the reasons for the termination. The Investigators will return the completed CRFs to Aptalis Pharma US, Inc.

In particular cases, the study may be terminated at a single investigational site, if the sponsor has relevant reasons (e.g., suspicion of fraud, lack of protocol compliance, lack of adherence to GCP, or no recruitment of subjects). In the case where a trial is discontinued, Aptalis Pharma US, Inc. will provide the Investigators with relevant procedures. Furthermore, the subject can withdraw from the study at any time without giving any reason.

Aptalis Pharma US, Inc. should promptly inform the regulatory authorities of all countries where the clinical study is being conducted (no later than 15 days in Canada and Europe) regarding the rationale for the termination of the study.

If the Investigator terminates his site participation in the study prematurely, the Investigator will provide a written statement as to why the study was terminated prematurely to Aptalis Pharma US, Inc.

The Investigator will complete a report notifying the REB/IRB/IEC of the conclusion of the clinical study. This report should be made within 15 days of completion or termination of the study. The final report sent to the REB/IRB/IEC will also be sent to Aptalis Pharma US, Inc. and, along with the completed CRFs, will constitute the final summary to Aptalis Pharma US, Inc. thereby fulfilling the Investigator's regulatory responsibility.

13 PUBLICATION POLICY

Aptalis Pharma designs and conducts clinical studies in an ethical and scientifically rigorous manner to determine the benefits, risks, and value of pharmaceutical products. Aptalis Pharma US, Inc is responsible for receipt and verification of data from all research sites for Aptalis Pharma US, Inc studies, to ensure the accuracy and integrity of the entire study database, which is owned by Aptalis Pharma US, Inc.

Aptalis Pharma US, Inc is committed to ensure that publication of all of its clinical studies results in biomedical journals are done in a timely manner, regardless of the study results. Publications should follow the guidelines established by the International Committee of Medical Journal Editors (ICMJE) and published in its Uniform Requirements of Manuscripts Submitted to Biomedical Journals (<http://www.icmje.org>). is committed to ensuring that authorship for all publications comply with the criteria defined by the ICMJE.

Clinical studies may involve already marketed products and/or investigational products. Aptalis Pharma US, Inc is committed to the timely submission and registration on a public database (e.g.Clintrials.gov) of summary information concerning relevant clinical studies that Aptalis Pharma US, Inc is conducting. These clinical studies will involve use of Aptalis Pharma US, Inc's marketed or investigational products. Aptalis Pharma US, Inc is also committed to the timely submission and posting of summary results of all clinical studies conducted in subjects involving the use of Aptalis Pharma US, Inc's products that are approved for marketing, or that are investigational products whose development programs are discontinued, regardless of outcome.

The publication rights of the investigators for this study are set forth in the individual agreements with each clinical sites.

16 APPENDICES

APPENDIX 1 – STUDY FLOWCHART

APPENDIX 2 – PHARMACOKINETICS BLOOD SAMPLING

APPENDIX 3 – CENTRAL NERVOUS SYSTEM ADVERSE EVENTS OF INTEREST

APPENDIX 1 - STUDY FLOWCHART

	Inclusion Visit (Day 0)	End of Visit (Day 11)	End of Study Visit (Day 39)
Informed Consent	X		
Demographics	X		
Inclusion/Exclusion criteria	X		
Vital Signs	X	X	X
Diagnostic tests done before Pylera® prescription ¹	X		
Co-morbidities, medical, surgical history	X		
Concomitant medications	X	X	X
Diagnostic H. pylori test (breath test, biopsy, or other test)	X		X ²
Pharmacokinetics sample	X	X ³	
Adverse events		X	X
CNS adverse events ⁴		X	X

1. Including information pertaining to prior *H. pylori* treatment.
2. At the discretion of the Investigator
3. Subjects who demonstrate bismuth accumulation at the End of Treatment Visit (> 50 µg/L) will be referred to the separate Intensive Monitoring Program to be evaluated for inclusion. In case of inclusion, patients will be requested to return to the laboratory to draw a third blood sample for evaluation of bismuth). In case of neurological AE indicative of bismuth encephalopathy (please refer to Appendix 3 – Central Nervous System Adverse Events of Interest) if present at Day 11 blood samples will be as quickly processed as possible.
4. For CNS adverse event indicative of encephalopathy, follow-up will be perform by Intensive Monitoring Program

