
Study Procedures:
	
This is a single-arm, open-label trial in presumed H. pylori-positive subjects and is restricted to centers in France.
 
Following identification of participating general practice and specialist study centers, subjects deemed eligible for study will be identified and may be enrolled. To assess eradication, subjects will complete a diagnostic H. pylori test (breath test, biopsy, or other test at the discretion of the Investigator) following a period of at least 28 days after the end of treatment.
 
Subjects who are treatment-eligible will already have a prescription for Pylera® and a PPI (presumed to be omeprazole) and will have been instructed on dosing as the dosing information contained within the Pylera® SmPC: 3 capsules Pylera® QID taken after meals and following a bedtime snack, and omeprazole capsule BID taken after breakfast and evening meal doses of Pylera®, for 10 days (equivalent to daily doses of 480 mg [as Bi₂O₃ equivalent], tetracycline hydrochloride 1500 mg, metronidazole 1500 mg, and omeprazole 40 mg).
 
Subjects will provide two blood samples for assessment of bismuth concentrations (total bismuth in plasma and whole blood and trimethylbismuth (TMB) in whole blood), with one sample provided prior to start of Pylera® treatment (D0) and one sample provided Day 11 i.e. Day 1 after completion of Pylera® treatment. If accumulation of bismuth is detected (defined as whole blood bismuth concentration exceeding 50 µg/L.), subjects will be contacted to immediately return to the laboratory to draw a third verification sample and will be referred for potential inclusion and follow-up in a separate intensive monitoring program. In case of a neurological AE indicative of bismuth encephalopathy (please refer to Appendix 3 – Central Nervous System Adverse Events of Interest) is present at Day 11 blood samples will be as quickly processed as possible.

	
A diagnostic H. pylori test to assess H. pylori eradication should be repeated on one single occasion at least 28 days post-treatment.

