3 STUDY DESCRIPTION (STUDY DESIGN)

3.1 OVERALL STUDY DESCRIPTION

This study is a multicenter, open-label, single-arm, clinical trial to be conducted exclusively in France and involving two hundred (200) eligible subjects. A detailed description of study procedures and study conduct is presented in Section 9 and Appendix 1 of this protocol.

The study will consist of an Investigator pre-selection period, and a subject treatment period.

The Investigator pre-selection period will identify likely prescriber profiles within a national reimbursement database (e.g., the EGB representative sample in France), or other applicable databases to determine the distribution of Gastroenterologists (GE) and General Practitioners (GP) based on appropriate measures including but not limited to the prescription of UBT or other diagnostic tests for *H. pylori*, or the prescription patterns of Pylera® when it is marketed.

[figure not shown]
This pre-selection analysis will also identify usage patterns per prescriber in order to evaluate the number of prescribers required to accrue the expected number of subjects without seeding.

Following identification of the GE/GP ratio and the calculation of sites required to complete recruitment within the 24 month timeframe, specific databases of health professionals such as CEGEDIM will be used to contact GPs and/or GEs to propose participation in the study as per the GE/GP prescriber ratio described above.

The subject study period will be conducted at these participating sites and will be comprised of three steps as follows:

1. Inclusion Visit (Day 0)
2. End of Treatment Period (EOT) Visit (Day 11)
3. End of Study (EOS) Visit (Day 39)

An allowance for participation will be provided to each patient at the end of the 3rd visit.

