3.2 SCHEDULING OF VISITS

Patient inclusion in the study will be considered after the decision to treat with Pylera® has been made by the Investigator.

The Inclusion Visit will be initiated following signature of Informed Consent.

Information regarding date of Pylera® prescription, name of prescribed PPI, demographic data, vital signs, height, weight, disease history for *H. pylori* infection (including information pertaining to prior *H. pylori* treatment), co-morbidities, medical and surgical history — will be surveyed, as well as information concerning diagnostic procedures performed to verify *H. pylori* infection.

Upon confirmation of eligibility, subjects will be given instructions for the first blood sample (D0 sample) for bismuth and TMB PK prior to initiating treatment with Pylera®, and an appointment for the second blood sampling.

Upon completion of the 10-day treatment with Pylera®, subjects will proceed to the EOT Visit to provide the second blood sample (D11 sample) for bismuth and TMB PK.

Subjects who demonstrate clinical symptoms indicative of bismuth-related neurological adverse events or bismuth accumulation at the EOT Visit (total bismuth in whole blood > 50 µg/L) will be requested to return to the laboratory immediately to draw a third blood sample for evaluation of bismuth. Subjects having clinical symptoms indicative of bismuth-related neurological adverse events will be referred to the separate Intensive Monitoring Program. If bismuth concentration remains sustained in subjects with no neurological symptoms and subject interview with Investigator confirms that no third-party source of bismuth was consumed outside of the context of this study, the subject will be referred to the separate Intensive Monitoring Program to be evaluated for inclusion.

A diagnostic *H. pylori* test (breath test, biopsy, or other test at the discretion of the Investigator) to assess *H. pylori* eradication should be repeated on one single occasion at least 28 days post-treatment as part of the EOS Visit.

Vital signs, concomitant medications, adverse events (AEs) and the presence of central nervous system (CNS) adverse events of interest as listed in Appendix 3 will be assessed at the EOT and EOS Visits.

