9.2.1 Subjects who completed treatment with Pylera®

Subjects who have completed the 10-day treatment with Pylera® will return to complete the following procedures as part of the EOT Visit:

- Vital signs measurement (blood pressure, pulse rate)
- Recording Pylera® treatment description and compliance
- Recording of concomitant medications
- Recording of AEs

The presence of CNS adverse events of specific interest as listed in Appendix 3 will be assessed at this visit with the specific form “Pharmacovigilance reporting form-neurological disorders and bismuth” developed for the collection of the adverse events of special interest as part of the Intensive Monitoring Program that will be completed by the Investigator.

Subjects will provide one blood sample as the post-treatment sample (D11 sample) for assessment of plasma and whole blood bismuth concentrations as well as whole blood TMB concentrations as per the procedures outlined in Appendix 2.

Subjects who demonstrate bismuth accumulation in whole blood at the EOT Visit ($> 50 \mu\text{g/L}$) will be requested to return immediately to the laboratory to draw a third blood sample for evaluation of bismuth. If bismuth concentration remains sustained and subject interview with Investigator confirms that no third-party source of bismuth was consumed outside of the context

of this study, the subject will be referred to the separate Intensive Monitoring Program to be evaluated for inclusion.

Subjects will return 28 days after the EOT Visit to complete the EOS Visit. At this visit, subjects will complete:

- Vital signs measurement (blood pressure, pulse rate)
- Recording eradication test
- Recording of concomitant medications
- Recording of AEs

The presence of CNS adverse events of specific interest as listed in Appendix 3 will be assessed at this visit with the specific form “Pharmacovigilance reporting form-neurological disorders and bismuth” developed for the collection of the adverse events of special interest as part of the Intensive Monitoring Program that will be completed by the Investigator.

Subjects who demonstrate a positive diagnostic *H. pylori* test (breath test, biopsy, or other test at the discretion of the Investigator) at End of Study will be documented by the completion of a specific form entitled “Targeted follow-up form – Pylera® eradication therapy failure”. These subjects will be referred to treatment for *H. pylori* infection outside of the context of this study.

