10.7 DATA SAFETY MONITORING BOARD

No Data Safety Monitoring Board is planned for this study.

Subjects who demonstrate a neurologic AE indicative of bismuth toxicity, will be evaluated by the Scientific Committee of a separate Intensive Monitoring Program. Such neurologic AEs of interest will include but are not limited to disorders in walking, speech and writing with psychiatric symptoms including mental confusion and myoclonia, tremor, and lack of coordination.

Subjects who demonstrate bismuth accumulation at the End of Treatment Visit ($> 50 \mu\text{g/L}$) will be requested to immediately return to the laboratory to draw a third blood sample for evaluation of bismuth. If bismuth concentration remains sustained and subject interview with Investigator confirms that no third-party source of bismuth was consumed outside of the context of this study,

	Page 41 of 96
	Protocol # : MA-PY-HpPK11-01

the subject will be referred to the separate Intensive Monitoring Program to be evaluated for inclusion.

The threshold for potential bismuth accumulation will be the Hillemand *et al.*²⁷ alert value of 50 µg/L, which will be defined as any accumulation value that is higher than 50 µg/L under the following formula:

$$\text{Accumulation Value} = (\text{EOT bismuth concentration} - \text{Day 0 bismuth concentration})$$

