An additional comparison will be made of all post-treatment concentrations in the omeprazole group versus post-treatment concentrations of all other PPIs pooled together. For each subject the C_{\min} will be grossly estimated assuming an elimination half-life of 19.95 hours³⁰ by the equation:

$$C_{\min} = \frac{C_{\text{observed}}}{e(-0.0347 * t)}$$

where t is the time elapsed between last dose intake and sampling time.

Individual observed results will also be classified as “above” or “below” the Hillemand *et al.*²⁷ alert threshold of 50 µg/L²⁷ for total whole blood bismuth concentrations solely as TMB has been calculated by Aptalis Pharma US, Inc. to exist at approximately 1:10,000 the level of average circulating bismuth concentrations.

For subjects who are already below 50 µg/L on Day 11, no other action will be performed and such subjects will be considered to have reached safe whole-blood levels within an acceptable time.

For subjects who are above 50 µg/L, the time required to reach 50 µg/L will be grossly estimated, again assuming an elimination half-life of 19.95 hours by the equation:

$$T_{recov} = \frac{\ln\left(\frac{50}{C_{min}}\right)}{-0.0347}$$

Such subjects will also be referred for evaluation and potential inclusion in the separate Intensive Monitoring Program.

The number of subjects requiring more than 24 hours to reach safe levels and the time required will be considered to draw conclusion on the clinical safety of Pylera® with regard to bismuth toxicity.

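### Appendix 1 footnote 3 makes the third blood sample conditional on inclusion in the Intensive Monitoring Program, whereas the rest of the protocol requires it at once for every subject above 50 µg/L

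*Protocol*

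**What the plan says.** **Third sample.** Appendix 1 footnote 3 sends subjects above 50 µg/L at End of Treatment (EOT) to the Intensive Monitoring Program for evaluation, and continues: "In case of inclusion, patients will be requested to return to the laboratory to draw a third blood sample for evaluation of bismuth". It gives no timing.

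Elsewhere the order is different:
- The Synopsis (Study Procedures) has the subject contacted to come back at once "to draw a third verification sample and will be referred for potential inclusion and follow-up in a separate intensive monitoring program".
- Section 3.2 asks for an immediate third sample when whole-blood bismuth exceeds 50 µg/L or when there are neurological symptoms suggestive of bismuth toxicity.
- Section 9.2.1 asks for an immediate return when whole-blood bismuth exceeds 50 µg/L.
- Section 10.7 says that subjects above the threshold "will be requested to immediately return to the laboratory to draw a third blood sample for evaluation of bismuth".
- Appendix 2 item 5 describes the sample as confirmatory, triggered by symptoms or by whole-blood bismuth above 50 µg/L.

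**Referral.** Section 3.2 refers symptomatic subjects directly: "Subjects having clinical symptoms indicative of bismuth-related neurological adverse events will be referred to the separate Intensive Monitoring Program". For the others it sets a condition: "If bismuth concentration remains sustained in subjects with no neurological symptoms and subject interview with Investigator confirms" that no outside source of bismuth was taken. Section 9.2.1 has the condition without the symptom split: "If bismuth concentration remains sustained and subject interview with Investigator confirms that no third-party source of bismuth was consumed". Section 10.7 repeats it. Section 11.7.7, speaking of all subjects above 50 µg/L, says: "Such subjects will also be referred for evaluation and potential inclusion in the separate Intensive Monitoring Program".

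**Status of the flowchart.** Section 3.1 states: "A detailed description of study procedures and study conduct is presented in Section 9 and Appendix 1 of this protocol". The opening of Section 9 says that the procedures are summarised in Appendix 1.

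**The concern.** The third sample exists to verify a high Day 11 value. In Sections 3.2, 9.2.1 and 10.7 the continued level helps to decide whether an asymptomatic subject is referred. In footnote 3 the sample comes after referral and only on inclusion, so no confirmatory value would be available when inclusion is decided, and subjects who are not included would have none at all.

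The primary objective (Section 2.1) is to verify that bismuth does not accumulate. Subjects above 50 µg/L are the ones in whom confirmation matters most. What is at stake is a safety procedure in those subjects and consistent handling of them across sites.

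**Working it through.** No figure in the protocol is in dispute, so the main check is a comparison of the current text.

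| Place | Trigger for third sample | Timing or condition | Referral of an asymptomatic subject above 50 µg/L |
|---|---|---|---|
| Synopsis | whole blood > 50 | immediate | yes, no further condition |
| Section 3.2 | whole blood > 50, or neurological symptoms | immediate | only if sustained and no other source |
| Section 9.2.1 | whole blood > 50 | immediate | only if sustained and no other source |
| Section 10.7 | > 50 | immediate | only if sustained and no other source |
| Section 11.7.7 | not addressed | not addressed | yes, no further condition |
| Appendix 1, footnote 3 | > 50 and included in the programme | after referral; no timing | yes, no further condition |
| Appendix 2, item 5 | whole blood > 50, or neurological symptoms | confirmatory; no inclusion condition | not addressed |

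**Case 1: above 50 µg/L, evaluated but not included.** The Synopsis, Sections 3.2, 9.2.1 and 10.7 and Appendix 2 all give a third sample. Footnote 3 gives none. No reading satisfies both.

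**Case 2: neurological symptoms.** Section 3.2 and Appendix 2 require a third sample. Footnotes 3 and 4 mention fast processing of the Day 11 samples and follow-up by the programme, but no third sample. This is an omission in the footnotes rather than a contradiction.

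**Case 3: asymptomatic, above 50 µg/L, level then falls or another bismuth product was taken.** The Synopsis, Section 11.7.7 and footnote 3 refer the subject for evaluation. Sections 3.2, 9.2.1 and 10.7 do not.

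**What the narrower referral rule could do in Case 3.** Inputs: elimination rate 0.0347 per hour (Section 11.7.7; it matches the stated half-life, since ln 2 / 19.95 = 0.0347) and the panic value of 100 µg/L for sustained concentrations (Section 1.1). Assumptions: sustained means that the third value is still above 50 µg/L, which the protocol does not state, and the third draw comes 24 or 48 h after the Day 11 draw, as no target time is given.

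Third value = Day 11 value × exp(−0.0347 × t)

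- Day 11 value 110, t = 24 h: 110 × exp(−0.8328) = 110 × 0.435 = about 48 µg/L
- Day 11 value 200, t = 48 h: 200 × exp(−1.6656) = 200 × 0.189 = about 38 µg/L
- Time for 100 to fall to 50: ln(100/50) / 0.0347 = about 20 h

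On these assumptions neither subject would be referred under Sections 3.2, 9.2.1 and 10.7, although both Day 11 values exceed 100 µg/L. The Synopsis, Section 11.7.7 and footnote 3 would refer both. This arithmetic bears only on the choice of referral rule; it does not measure the conflict over the third sample.

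**The case against.** The best defence is that footnote 3 is a lone outlier. Section 9 calls the flowchart a summary, and a site that also reads Sections 3.2, 9.2.1 and 10.7 and Appendix 2 will draw the sample. This stands in part: it is why the site could, rather than would, omit the sample. It does not remove the conflict, because Section 3.1 names Appendix 1 together with Section 9 as the detailed description, and no order of precedence is stated. The footnote is in the current Appendix 1. The Amendment No. 2 table shows both it and the immediate-return wording of Section 9.2.1 as new text, so the log does not show which was meant to prevail.

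A second defence is that the referral differences are mostly shorthand, since every version leads only to evaluation for inclusion. This is largely right. Symptomatic subjects reach the programme under Section 3.2, and Sections 9.2.2, 10.4.3.3 and 10.7 and footnote 4 point the same way. A reader might infer that their referral is also in dispute; the text does not support that. The remaining split is Case 3.

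A reader might also infer that Section 3.2's referral rule should simply be adopted throughout because it is the most detailed. The protocol does not show that the narrower rule was intended, and the 110 and 200 µg/L examples show its possible cost.

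**Conclusion.** The contradiction over the third sample is real and should be corrected. It is a fault of safety procedure. A reader might infer that the pharmacokinetic results are compromised, but the Day 0/Day 11 description, the classification above or below 50 µg/L and the estimated recovery time do not use the third sample.

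The number of subjects affected cannot be derived from the protocol and is probably small. In the earlier study described in Section 1.1, the average 24-hour trough plasma level was 4.66 µg/L, and no subject had sustained levels above approximately 20 µg/L. Symptomatic subjects also have their Day 11 samples processed as quickly as possible.

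The referral split is a separate, narrower point. It is established from the text alone; the 110 and 200 µg/L examples rest on the assumed delays, the assumed meaning of sustained and the protocol's own rough elimination rate.

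**What to change.** 1. Rewrite footnote 3: every subject with whole-blood bismuth above 50 µg/L at EOT, or with neurological symptoms indicative of bismuth toxicity, returns immediately for the third sample, before and regardless of any decision on inclusion in the Intensive Monitoring Program. This matches Section 3.2 and Appendix 2 item 5.

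2. Have the sponsor's safety physicians choose one referral rule for asymptomatic subjects above 50 µg/L whose level falls or who took another bismuth product. State it identically in the Synopsis, Sections 3.2, 9.2.1, 10.7 and 11.7.7, and Appendix 1. If the conditional rule is kept, they should confirm that they accept non-referral of some subjects with Day 11 values above 100 µg/L, and say what sustained means. The wording should also settle whether the threshold applies to the measured EOT value or to EOT minus Day 0, as in the Section 10.7 formula.

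**Cost.** The first change adds no sample beyond those that Section 3.2 already requires. Both need a protocol amendment, with ethics approval where Section 7.8 applies. The second also touches a programme that belongs to the Risk Management Plan (Section 10.4.3.3), so it needs a safety decision and not only editing.
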